8.3.1 Inclusion Criteria

Subjects **must** meet all of the following criteria to be eligible for the study:

1. Men or women 22 years of age or older.
2. Two fully visible bilateral nasolabial folds each with a Wrinkle Severity Rating Scale Score of 3 or 4 that may be corrected with an injectable dermal filler.
3. If female and of childbearing potential, a negative urine pregnancy test and agree to use adequate contraception. Female subjects of childbearing potential (excluding women who are surgically sterilized or postmenopausal for at least 2 years) must have a negative urine pregnancy test and must be willing to use a medically accepted method of contraception during the study. The following are considered acceptable methods of birth control for the purpose of this study: oral contraceptives, contraceptive patches, contraceptive implant, vaginal contraceptive, double barrier methods (e.g., condom and spermicide), contraceptive injection (Depo-Provera®), intrauterine device (IUD), hormonal IUD (Mirena®), and abstinence with a documented second acceptable method of birth control if the subject becomes sexually active. Subjects entering the study who are on hormonal contraceptives must have been on the method for at least 90 days prior to the study and continue the method for the duration of the study. Subjects who had used hormonal contraception and stopped must have stopped no less than 90 days prior to Visit 1/Day 1.
4. Ability to understand and comply with the requirements of the study.
5. Willingness and ability to provide written informed consent.
6. Agree to refrain from seeking other treatment for this condition during the study.

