8.3.2 Exclusion Criteria

Subjects who meet any of the following criteria will be excluded from the study:

1. Wrinkle Severity Rating Scale Score of ≤ 2 on the right or left nasolabial fold.
2. Women who are pregnant or lactating.
3. Received prior dermabrasion, facelift, or Botox below the orbital rim within 6 months (180 days) prior to entry into the study.

4. Previous tissue augmentation (bulking agents) for facial wrinkles and scars within 6 months (180 days) at the proposed injection sites.
5. Previous tissue augmentation with permanent implants.
6. Evidence of scar-related disease or delayed healing activity within the past 1 year.
7. Scars at the intended treatment sites.
8. History of keloid formation or hypertrophic scars.
9. Any infection or wound on the face.
10. Allergic history including anaphylaxis or multiple severe allergies to natural rubber latex or lidocaine.
11. Aspirin or nonsteroidal anti-inflammatory drugs within 1 week (7 days) prior to treatment.
12. Concomitant anticoagulant therapy, antiplatelet therapy, or history of bleeding disorders or connective tissue disorders.
13. Over-the-counter (OTC) wrinkle products or prescription wrinkle treatments within 4 weeks (28 days) prior to treatment and throughout the study.
14. Immunocompromised or immunosuppressed.
15. Clinically significant organic disease including clinically significant cardiovascular, hepatic, pulmonary, neurologic, or renal disease or other medical condition, serious intercurrent illness, or extenuating circumstance that, in the opinion of the investigator, preclude participation in the trial.
16. Received any investigational product within 30 days of signing the Informed Consent Form.
17. Facial tattoo that may interfere with diagnosis.
18. Systemic (oral/injectable) corticosteroids or immunosuppressive medications within 30 days prior to treatment and topical steroids on the face within 14 days prior to treatment start and throughout the study.

8.3.3 *Subject Withdrawal Criteria*

A subject may withdraw from the study at any time for any reason.

A subject will be withdrawn from the study if his/her safety or well-being is determined to be at risk. Withdrawal will be made at the discretion of the investigator or at the subject's request.

A subject must withdraw from the study for any of the following reasons:

- The subject or legal representative withdraws consent
- The subject's product code is unblinded
- There is a significant protocol violation

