8.4.7 Prior and Concomitant Medications/Treatments

All medications and other treatments taken by the subject within 6 months before Visit 1/Day 1 and during the study are to be recorded on the CRF using their generic name, if known, with the corresponding indication. The medications to be recorded include prescription and OTC medications and dietary supplements. All medications taken on a regular basis, including vitamins, aspirin, and acetaminophen, should be recorded prior to first use of the study medication.

The use of any concomitant medication must relate to the subject's documented medical history, prophylaxis, or an AE.

8.4.7.1 Medications, Supplements, and Other Substances Prohibited Before Study Entry and During the Study

The medications prohibited prior to Visit 1/Day 1 are listed in the exclusion criteria ([Section 8.3.2](#)).

Subjects will be advised to avoid the following for the duration of the study:

- Botox® in the study treatment areas
- Any chemical peel (light, medium or deep) in the study treatment areas
- Soft tissue augmentation anywhere on the face
- Dermabrasion or laser abrasion anywhere on the face
- Silicone injections or implants anywhere on the face
- Facial wrinkle therapies, including Accutane® and Renova®
- Aesthetic facial surgery (i.e., facelift)
- Oral corticosteroids or immunosuppressive medications
- Topical corticosteroids on the face

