8.5 Study Schedule

The visit-by-visit schedule of study activities is provided in the Study Flow Chart in [Section 3.2](#). The timing of each visit is relative to Day 1, which is defined as the day the subject is randomized and treated.

All visits should be performed within the windows specified on the Study Flow Chart. Every attempt should be made to have each subject attend each visit as scheduled. If a subject is unable to attend a visit within the specified window the visit should be scheduled as closely as possible to the applicable window.

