9.1 Analysis Populations

Three populations are defined for the analyses.

- Intent-to-treat (ITT) (safety population): All randomized subjects who received study product.
- Modified intent-to-treat (mITT): All randomized subjects who met the inclusion/exclusion criteria, were randomized, received both study products, and returned for at least 1 post-injection assessment of WSRS score from both sides of the face.
- Per-protocol (PP): All randomized subjects who met all inclusion/exclusion criteria; received both study products; completed Visit 6/Week 24 within the specified window, had data on WSRS score from both sides of the face, and had no significant protocol violations that would affect the treatment evaluation.

Efficacy analyses will be performed on the mITT and PP populations. Safety analyses will be performed on the ITT population.

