9.4 Efficacy Evaluations

The primary efficacy variable is change from Baseline to Week 6/Week 24 in WSRS score. Summary statistics (mean, SD, minimum, median, maximum) and 95% confidence interval (CI) will be presented for the changes scores for each treatment and for the difference in change scores between the two treatment groups (Comparator minus Test product, i.e., Restylane minus Revanesse). The 95% CI for difference between treatments will be constructed assuming a normal distribution of the change scores. If the upper bound of this 95% CI is less than the pre-specified non-inferiority (NI) limit (i.e. 0.50), the Test product will be claimed to be non-inferior to the Comparator product.

Secondary efficacy endpoints include the responder rate, i.e., the percentage of subjects with treatment success (defined as at least a 1-grade improvement in WSRS from baseline to Week 24), pGAI score at Visit 6/Week 24, and iGAI score at Visit 6/Week 24. For these secondary variables, the null hypothesis to be tested is that there is no difference between the two products. The variables responder rate, pGAI and iGAI scores at Visit 6/Week 24 will be tabulated with frequencies and percentage and analyzed using the Wilcoxon matched-pairs signed rank test.

Other efficacy variables include change in WSRS score, pGAI, and iGAI at Visit 2/Week 1, Visit 3/Week 2, Visit 4/Week 4, and Visit 5/Week 12. Treatment difference with respect to these variables will be examined using descriptive summaries.

All efficacy analyses will be performed for both the PP and mITT populations. For the primary endpoint, the results from PP are considered definitive and those from mITT supportive.

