9.6 Sample Size Determination

In a previous Prollinium split-face study of Revanesse Ultra versus Restylane, following were achieved with respect to the Investigator WSRS score:

	N	Revanesse (Mean \pm SD)	Restylane (Mean \pm SD)
WSRS Before Injection	110	3.22 \pm 0.42	3.20 \pm 0.50
WSRS at Month 6	110	2.34 \pm 0.79	2.41 \pm 0.81

From these statistics, the difference between Revanesse and Restylane (Restylane minus Revanesse) in change from baseline WSRS to Month 6 is estimated to have a mean value of -0.095 with an approximate standard deviation (SD) of 1.30.

Therefore, about 63 per-protocol (PP) subjects will supply a power of 85% with respect to change from baseline to Month 6 in WSRS score based on the following:

- The non-inferiority limit is 0.50. If the upper bound of the 95% confidence interval (CI) treatment difference (Comparator – Test) is less than 0.50 for the PP population, the Test product will be claimed to be non-inferior to the Comparator product.

- The difference between Comparator and Test (i.e., Comparator – Test) has a mean value of 0, with a standard deviation of 1.30.

A total of 163 subjects will be enrolled into the study to provide adequate data for monitoring the safety of the study product.

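### The non-inferiority claim is decided by the per-protocol set alone, whose membership depends on events after injection, so a failing mITT result cannot block it

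*Protocol*

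**What the plan says.** Section 9.4 ranks the two efficacy sets for the primary endpoint: "For the primary endpoint, the results from PP are considered definitive and those from mITT supportive". The synopsis repeats this ranking. Section 9.6 attaches the decision to PP explicitly: if the upper bound "is less than 0.50 for the PP population, the Test product will be claimed to be non-inferior to the Comparator product". No passage says what follows if PP passes and mITT does not.

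Under section 9.1, a PP subject must be eligible and have received both products. The subject must also have "completed Visit 6/Week 24 within the specified window, had data on WSRS score from both sides of the face" and have "had no significant protocol violations that would affect the treatment evaluation". The Week 24 window is ±7 days (section 3.2). The mITT set has no window criterion. It requires eligibility, both products and one post-injection WSRS score from both sides, and section 9.2 fills its missing efficacy values by LOCF.

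Three other passages bear on who leaves PP:
- Inclusion criterion 6 (section 8.3.1) reads "Agree to refrain from seeking other treatment for this condition during the study", and section 8.4.7.1 lists "Soft tissue augmentation anywhere on the face" among the things subjects are advised to avoid.
- Section 8.3.3 gives "There is a significant protocol violation" as a reason for which a subject must withdraw, and section 8.3.4 says withdrawn subjects are not replaced.
- Section 8.5 asks sites to hold late visits anyway: "If a subject is unable to attend a visit within the specified window the visit should be scheduled as closely as possible".

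**The concern.** Completion of Week 24, timing of that visit and protocol violations are all settled after injection, so they can depend on how the folds have done. A subject with a disappointing fold may stop attending, or may seek other treatment and so commit a violation. Either route removes the subject from the only analysis that decides the claim. Blinding does not close these routes, because a subject who does not know which product is where can still see that one fold has failed.

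An exclusion removes both folds, so the pairs stay balanced. The PP mean is nevertheless biased if exclusion is related to the between-fold difference and runs more toward test-fold failures. The sole confirmatory claim would then rest on a favourable subset, and the mITT analysis, which keeps such subjects if they have a post-injection score, has no power to stop it.

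**Working it through.** **Sign.** I take change as improvement, so a positive Comparator minus Test value means the test product is worse. This matches section 9.6: from its table, (3.20 − 2.41) − (3.22 − 2.34) = −0.09, against the stated −0.095.

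**The plan's own figure.** Inputs from section 9.6: limit 0.50, true difference 0, SD of the paired difference 1.30, 85% power, two-sided 95% interval (one-sided 0.025).
- Normal formula: (1.30 × (1.960 + 1.036) / 0.50)² = 60.7, so 61.
- Noncentral t (df n − 1, noncentrality 0.50 × √n / 1.30): the first n with at least 85% power is 63, at 85.2%.

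The stated 63 is reproduced. Since 63/163 = 38.7%, up to 100 of 163 subjects could leave PP and the test would keep its planned power. Poor PP retention would therefore not in itself prevent a claim.

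**What selective exit would do.** The protocol gives no exclusion rate, so f and d below are assumptions. Let the full-set mean difference be exactly 0.50, so that any claim is false. Let a fraction f leave PP with mean difference d.
- PP mean = (0.50 − f × d) / (1 − f)
- Shift toward the claim = f / (1 − f) × (d − 0.50)
- False-claim probability: noncentral t with noncentrality (0.50 − PP mean) × √n / 1.30, where n = 163 × (1 − f), rounded, and the SD is kept at 1.30

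| f | d | PP n | Shift | PP mean | False-claim rate |
|---|---|---|---|---|---|
| 5% | 1.0 | 155 | 0.026 | 0.474 | 4.4% |
| 5% | 1.5 | 155 | 0.053 | 0.447 | 7.2% |
| 5% | 2.0 | 155 | 0.079 | 0.421 | 11.3% |
| 10% | 1.0 | 147 | 0.056 | 0.444 | 7.4% |
| 10% | 1.5 | 147 | 0.111 | 0.389 | 17.6% |
| 10% | 2.0 | 147 | 0.167 | 0.333 | 33.9% |

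If the excluded subjects have the same mean difference as the rest (d = 0.50), the shift is 0 and the rate stays at 2.5%. If exits after test-fold and comparator-fold failures are equally frequent and equally large, d = 0. That gives no shift when the products are equal. At the boundary it moves the PP mean away from the claim (0.50 / 0.95 = 0.526 for f = 5%).

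**Cost of requiring both sets.** Power with true difference 0 and SD 1.30, by noncentral t, is 99.8% at n = 163, 99.6% at 147 and 99.2% at 130. Adding an mITT condition can lose at most the probability that mITT fails: 0.2, 0.4 and 0.8 points respectively, whatever the PP size.

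**The case against.** Making PP primary is common in non-inferiority trials because a full set can dilute a real difference. The protocol states the choice openly and runs every efficacy analysis in both sets, so a discordant mITT result would be reported. This justifies keeping PP in the rule. It does not justify letting PP decide alone, since being reported is not the same as being able to block the claim.

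A reader might infer that the PP analysis is biased toward non-inferiority as such. The documents do not support that. Sides are randomised, subjects are blinded, each exclusion removes both folds, and a failed comparator fold can prompt the same exit. The only earlier data in the protocol show similar Month 6 scores (2.34 and 2.41, section 9.6), which gives no sign of an excess on the test side. Several provisions also weaken the route: the Week 1 touch-up (8.6.11), the open-label treatment offered at Week 24 (8.4.3), which gives a reason to attend, and the end-of-study assessments including WSRS for subjects who withdraw (8.3.3, 8.7.3, 8.9.6.1). This stands, and it makes the bias conditional.

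A reader might also infer that the ±7-day window distorts the comparison, or that it is harmless and should be widened. Neither follows. Both folds are scored at the same visit, so a late date is shared, and dropping such pairs costs mainly a little precision (99.8% power at 163 against 99.6% at 147). If the products fade at different rates, though, a late visit measures a different time point. The mITT set already has no window criterion.

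Section 9 leaves detailed data handling to the SAP, which may define a significant violation. The decision rule itself, however, is fixed in the protocol.

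**Conclusion.** The point holds as a weakness in the decision rule: PP alone decides, PP membership depends on post-injection events, and the claim survives a failed mITT analysis. The sample size is correct and is not at issue.

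The harm is possible, not shown. It needs exits related to the between-fold difference that are more frequent or larger on the test side. Under the assumed 5–10% exclusion and mean deficit of 1–2 grades, at a true difference of 0.50 and SD 1.30, the PP mean shifts by 0.03–0.17 and the false-claim rate goes from 2.5% to about 4–34%. These figures illustrate sensitivity and do not estimate what this trial will show. The change is worth making because it closes the gap at almost no cost.

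**What to change.** In the synopsis, section 9.4 and section 9.6, state that non-inferiority is claimed only if the upper 95% limit for Comparator minus Test is below 0.50 in both the PP and the mITT populations.

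The mITT set as written is not a full safeguard. It removes ineligible subjects, and LOCF can carry an early good score past a later failure. So also state that:
- Week 24 scores taken outside the window but before any retreatment are used as observed in mITT; and
- a sensitivity analysis of the primary endpoint handles missing Week 24 scores without relying on LOCF.

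The PP window can stay as it is. The cost is wording and a slightly stricter success rule: under one point of power with 130–163 subjects in mITT when the true difference is 0. Because PP stays in the rule, the change can only lower the chance of a false claim.

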9.4.1 Interim Analysis

No formal interim analysis is planned.

9.5 Safety Analyses

Adverse events will be coded using the Medical Dictionary for Regulatory Activities (MedDRA, Version 15.1 or higher).

TEAEs are defined as events that appear subsequent to the first injection or that were present prior to the first injection but worsened in intensity after the first injection. TEAEs may include, but are not limited to, injection site bruising, injection site discoloration, injection site edema, injection site erythema, injection site inflammation, injection site pain, and injection site swelling.

Frequency and percent of subjects reporting TEAEs of injection site reactions will be tabulated for each treatment by preferred terms, and further by severity. In summaries of severity, subjects who reported more than one event in a treatment arm that are mapped to the same preferred term will be counted only once in that treatment arm under the strongest severity.

For other AEs where an association with either treatment may not be clearly identified, including systemic TEAEs, frequency and percent of subjects will be tabulated to treated subjects as one group by preferred terms and system organ class, and further by severity and relationship to study device. In summaries of severity and relationship, subjects who reported more than one event that are mapped to the same preferred term will be counted only once under the strongest severity and relationship.

Adverse events will be summarized using the ITT population.

SAEs will be discussed within the clinical study report. Data collected pertaining to SAEs will be presented in data listings.

Concomitant medications will be classified according to the World Health Organization (WHO) Drug Dictionary (March 2013 edition) and will be presented in data listings.

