8.2 Beginning and End of Study

A subject is considered to be enrolled in the study when he/she has provided written informed consent and has been randomized to treatment.

A subject who is not retreated at Week 24 is considered to have completed the study after he/she has completed Visit 6/Week 24. A subject who is retreated at Week 24 is considered to have completed the study after he/she has completed Visit 8/Week 52.

A subject is considered to have withdrawn after he/she has withdrawn consent or has been withdrawn under the conditions specified in [Section 8.3.3](#).

A subject is considered to have been lost to follow-up if he/she cannot be contacted by the investigator. The investigator will document efforts to attempt to reach the subject twice by telephone and will send a certified letter before considering the subject lost to follow-up. The end of participation for a subject lost to follow-up is documented as the date of the certified letter.

Each subject will be monitored for the occurrence of AEs, including serious adverse events (SAEs), starting immediately after the subject has signed the informed consent form (ICF). Each subject will be followed for safety monitoring until he/she is discharged from the study.

Follow-up procedures related to pregnancy, AEs, or SAEs may continue beyond the end of the study.

Each subject will participate in the study for approximately 24 weeks (if not retreated at Week 24) or approximately 52 weeks (if retreated at Week 24) from the time he/she signs the ICF through the final contact. After determination of eligibility at Visit 1/Day 1, each subject will be treated with Revanesse Ultra and Restylane.

It is anticipated that the duration of this study will be 24 months.

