The subject should be injected so that an optimal correction is achieved. If overcorrected, massage firmly between fingers or against underlying bone to obtain optimal results. Approximately 20% overcorrection can be massaged out; more will lead to a persistent unwanted cosmetic result.

Optional Retreatment at 6 Months

At Visit 6/Week 24, the subject may be retreated with Revanesse Ultra, and treatment will be open-label. Subjects will be eligible for retreatment when WSRS scores have returned to baseline for either or both NLFs. If scores have not returned to baseline, subjects are also eligible to be injected for either one or both NLFs as needed to achieve optimal correction. The retreatment group and the optimal correction group will be separated for data analysis.

8.4.4 *Blinding of Study Product*

Injections of the study product prior to Week 24 are performed by the unblinded injecting investigator. The blinded evaluator is not allowed to retrieve study supplies or to be present during opening of the study supplies or during the injections. The injecting investigator is not to have any discussion with the blinded evaluator or subjects regarding the treatments.

Subjects are blinded to treatment assignment of each NLF. Subjects are physically masked (blindfolded) just prior to and during all injection procedures to prevent observation of the syringes containing study product.

Subjects, investigators, the sponsor's staff conducting the study, and members of the administrative team will not have access to individual subjects' treatment assignments. In the event of an emergency that requires breaking of the study blind, randomization code envelopes will be maintained by each investigator that can be opened to reveal the study product.

See [Section 8.9.6.2](#) for a description of the method of unblinding a subject during the study if such action is warranted.

Retreatment with Revanesse Ultra at Week 24 is unblinded. Subjects being retreated do not need to be masked and retreatment may be administered by a qualified investigator or evaluator.

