8.6.14 Subject Diary Card

A diary card will be dispensed to each enrolled subject at Visit 1/day 1. The subject will be instructed to complete the diary card to record any AEs experienced during the 2 weeks after receiving treatment. The diary card will be collected at Visit 3/Week 2. A diary card will be dispensed at Visit 2/ Week 1 if a touch-up treatment is administered and at Visit 6/ Week 24 if retreatment is done. The diary card will be collected at Visit 4/Week 4 and Visit 7/Week 28 if applicable.

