8.9 Assessment of Safety

8.9.1 Safety Endpoints

Safety of the study products will be compared by evaluating the nature, severity, and frequency of treatment-emergent adverse events (TEAEs). All AEs that occur during the study will be recorded whether or not they are considered to be related to treatment. A description of the AE will be recorded with the date of onset, date of resolution, severity of the AE, relationship to the study product, action taken, and the outcome.

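### Section 9.5 starts the by-treatment table of injection-site events at the first injection and never closes it, so reactions to the optional open-label Week 24 Revanesse Ultra injection fall into the product comparison

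*Protocol*

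**What the plan says.** Protocol Section 8.9.1 makes the safety evaluation comparative: "Safety of the study products will be compared by evaluating the nature, severity, and frequency of treatment-emergent adverse events (TEAEs").

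Section 9.5 sets the counting rule. "TEAEs are defined as events that appear subsequent to the first injection or that were present prior to the first injection but worsened". No closing date is given. The section then sets the table: "Frequency and percent of subjects reporting TEAEs of injection site reactions will be tabulated for each treatment by preferred terms", with a split by severity. A subject with several events under one preferred term "will be counted only once in that treatment arm under the strongest severity". All adverse event summaries use the ITT population, and no study period is named.

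Section 8.4.3 offers open-label Revanesse Ultra at Week 24. Return of the WSRS score to baseline qualifies a fold. Where scores have not returned, "subjects are also eligible to be injected for either one or both NLFs as needed to achieve optimal correction". A fold randomised to Restylane can therefore receive Revanesse Ultra. The same section adds: "The retreatment group and the optimal correction group will be separated for data analysis".

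Reactions to this injection are collected. Section 8.2: "A subject who is retreated at Week 24 is considered to have completed the study after he/she has completed Visit 8/Week 52". Section 8.9.3 continues safety follow-up until discharge. Under Section 8.6.14 a further diary card is given at Visit 2 "if a touch-up treatment is administered and at Visit 6/ Week 24 if retreatment is done".

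The opening of Section 9 leaves fuller methods and data handling rules to the SAP.

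**The concern.** Up to Week 24 the safety comparison is well protected. Each subject receives both products, the side is randomised, subject and evaluator are blinded, and Section 8.4.3 asks for similar technique and volume on both sides. After Week 24 only one product is injected. It is optional, open-label, and may go into one fold or both.

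With no end to the window, the 9.5 table mixes the two kinds of exposure. Because a subject is counted at the strongest severity, a Week 24 reaction can also raise the severity of an event already counted. Section 9.5 does not say whether such a reaction belongs to the product injected or to the arm first assigned to that fold. The two choices distort the table in different ways.

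The stake is the safety half of the study objective in Section 7. Section 9.6 needs about 63 per-protocol subjects for efficacy and enrols 163 in order to have adequate safety data.

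**Working it through.** The plan gives no figure on this point. Its one computed figure, 63 per-protocol subjects at 85% power, reproduces (paired t, margin 0.50, mean 0, SD 1.30: power 85.2% at n = 63) and is not affected.

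**Inputs**

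- Uptake u: not given for this trial. Assumed 25% to 80%. The upper value is the share of eligible subjects retreated in the Restylane lip study (Section 15.2), a different site on the face. The lower value is purely an assumption.
- Risk per fold injection p, common reactions: one-side diary rates after initial Restylane treatment in the split-face study 31GE0003 (Section 15.2, Tables 1 and 2), from itching 30% to swelling 87%. Section 8.9.3 of this trial does not allow specific events to be elicited, so these may be too high.
- Risk, less common reactions: Table 9 gives discoloration 4%, pain 5% and swelling 24% per patient. Those patients had both folds injected at baseline, one reinjected at 4.5 months and the other at 9 months, so the rates accumulate over at least four fold injections. Under independence, p = 1 − (1 − rate)^(1/4): 4% becomes 1.0%, 5% becomes 1.3%, 24% becomes 6.6%.

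**Booked by product, identical products, no touch-up**

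Without retreatment both columns show p. With both folds retreated, the false Revanesse excess is u[(1 − p) − (1 − p)³]. With one fold retreated it is u·p(1 − p). In percentage points, at u = 25% and 80%:

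| p | both folds | one fold |
|---|---|---|
| 1.0% | 0.5 / 1.6 | 0.3 / 0.8 |
| 1.3% | 0.6 / 2.0 | 0.3 / 1.0 |
| 6.6% | 3.0 / 9.6 | 1.5 / 5.0 |
| 30% | 8.9 / 28.6 | 5.3 / 16.8 |
| 87% | 3.2 / 10.2 | 2.8 / 9.0 |

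Three departures from these assumptions reduce the 30% both-fold result of 8.9 / 28.6:

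- Within-subject correlation (beta-binomial): 5.9 / 18.9 at 0.3, and 4.1 / 13.2 at 0.5.
- Lower risk on repeat injection. In the lip study 87% of subjects had events after the first treatment and 65% after the second, a ratio of 0.75. Repeat risk becomes 0.30 × 65/87 = 0.224, and u(0.70)[1 − (0.776)²] = 7.0 / 22.3. The same insert reports repeat reactions similar to initial ones in study 31GE0003, so equal risk is also defensible. No figure is given for repeat Revanesse Ultra.
- Every subject touched up in both folds at Week 1: u[(1 − p)² − (1 − p)⁴] = 6.2 / 20.0.

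**Booked by fold**

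Let pT and pC be the per-injection risks of Revanesse Ultra and Restylane. With both folds retreated, the difference between columns is (pT − pC)(1 − u·pT).

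- If pT = pC, it is zero.
- Otherwise the true difference shrinks by the share u·pT: 7.5% to 24% at pT = 30%. For true rates of 50% against 30%, the 20 points become 17.5 at u = 25% and 12.0 at u = 80%.

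If only one fold is retreated, that fold's arm gains u·p(1 − p), or 5.3 / 16.8 points at 30%. If it is the Restylane fold, Revanesse Ultra reactions count against Restylane.

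**After a cut-off at the Week 24 injection**

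With equal risk per injection and no touch-up, both columns equal p and the false difference is zero.

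**The case against.** The strongest reply is that periods for safety tables, and the column for open-label events, are usually settled in the SAP, to which Section 9 defers. This limits the point but does not remove it. Section 9.5 is not silent: it fixes a start, a population, a by-treatment table and a counting rule, and that rule has no end. A reader might infer that the final tables will pool the two periods. The protocol does not show this, because the SAP may set the cut-off.

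Second, the separation sentence in 8.4.3 shows that retreated subjects were meant to be handled apart. It does, but it divides two retreated groups from each other by WSRS status. It does not divide before from after Week 24, nor one fold history from another, and 9.5 does not repeat it.

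Third, the arms in a split-face trial are the randomised folds, so booking by product is only one reading. This stands. A reader might infer that Revanesse Ultra will look 20 to 29 points worse. That needs booking by product, which 9.5 does not prescribe, with both folds retreated, independence, high uptake and a common reaction.

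Fourth, the Table 9 rates might be read as risk per injection, which at 5% would give an excess of 2.3 to 7.4 points. They are cumulative, and the supported range is 0.6 to 2.0.

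**Conclusion.** The point holds as a fault in the protocol wording. Followed as written, 9.5 lets reactions to an optional, open-label injection of one product into the randomised safety comparison, and nothing else in the protocol closes the window.

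Direction and size are not determined by the documents. Booked by product, the false Revanesse excess runs from roughly 0.5 to 2 points for uncommon reactions to possibly 20 or more for common ones under independence and high uptake. Correlation, lower repeat risk or retreatment of one fold only makes it smaller. Booked by fold, there is no false difference if both folds are retreated, but a true one is diluted by up to about a quarter at 30% risk. Retreating one fold adds events to that fold's arm only. All of this rests on assumed uptake and on Restylane rates from other studies.

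The consequence is moderate. The table is descriptive, with no safety test planned. It would be wrong to infer any harm to the primary analysis: Week 24 WSRS is assessed before retreatment.

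A separate matter should not be read as support for this point. Section 8.4.3 allows Revanesse Ultra in a fold first given Restylane even when the score has not returned to baseline, while the insert in Section 15.1 carries a precaution about areas that already hold another filler. The sponsor needs to reconcile these passages.

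**What to change.** In Section 9.5, limit the by-treatment table of injection-site events to those with onset before the Visit 6 retreatment injection, and keep all events for subjects who are not retreated. Tabulate later injection-site events separately by fold history: Restylane then Revanesse Ultra, and Revanesse Ultra then Revanesse Ultra. If the SAP already does this, bring 9.5 into line with it.

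The cost is one sentence and one extra table. Onset dates are recorded under Section 8.9.1 and the product used in each fold under Section 11.2.1, so no visit, subject or assessment is added and the sample size does not change.
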